### 7.2.2. Secondary Study Outcome Measures

1. Safety and feasibility. Safety endpoints are described in 7.2.3. For feasibility, are patients willing and able to take both daily oral FMT capsules or the one day FMT treatment? What are recruitment and retention rates for each group?
2. Recurrence of CDI: Does the patient develop a CDI during the course of the study, assessed through clinical symptoms and PCR for the *C. difficile* toxin in the stool samples collected as described in 7.2.1? If the patient develops a CDI during the study period, what is the time (in days) from randomization into the study to the CDI?
3. *C. difficile* colonization: Is the patient colonized or do they become colonized with *C. difficile* at any point during the study? *C. difficile* colonization will be detected by the presence of *C. difficile* via PCR. If the patient becomes colonized, what is the time (in days) from randomization into the study to colonization?

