**Reference therapy** Placebo: 5 capsules of oral placebo per day undergoing antibiotic treatment and for 7 days following conclusion of antibiotic treatment.

**Statistical Methodology** All data will be analyzed using SAS and R. Patient characteristics will be summarized using descriptive statistics. To assess changes in the gut microbiota, ANCOVA and linear mixed models will be used for longitudinal measurements. Safety and adverse events will be summarized using descriptive statistics.

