### **6. STUDY OBJECTIVES AND PURPOSE**

The goal of this study is to assess the effect of daily oral FMT and a single dose FMT on the gut microbiota in patients currently undergoing antibiotic treatment.

- Primary Objective: To assess the efficacy of oral FMT on the composition and function of the gut microbiota compared to the placebo groups.
- Secondary Objective: To assess the safety and feasibility of both oral FMT regimens versus placebo.
- Secondary Objective: To determine the rate of CDI during oral FMT versus placebo.
- Secondary Objective: To determine the rate of *C. difficile* colonization during oral FMT compared to placebo.
- Secondary Objective: To evaluate time to CDI and/or colonization with *C. difficile*.

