#### **12.3. Final Analytic Plan**

Categorical data will be described using descriptive statistics (proportions and percentages). Continuous data will be described using means and standard deviations (normally distributed data) or using medians and interquartile range (non-parametric data). Appropriate comparative statistical tests will be chosen based

in the variable types (categorical, dichotomous, continuous) and distribution (parametric, non-parametric) and will be used to describe significant differences between intervention and control groups. Where appropriate, point estimates and confidence intervals will be reported. The p-value will be two tailed with a significance level of 0.05.

The microbiome will be assessed using 16s rRNA targeted amplicon sequencing. Sequences will be cleaned and binned into operational taxonomic units and assigned taxonomy. Differences within individuals will be assessed using the Inverse Simpsons Diversity index and comparisons between study groups will be done using the Bray Curtis dissimilarity matrix and visualized using principal coordinates analysis.

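### Time to CDI and time to colonization are defined only for patients who have the event, and no censored-data method is named, so the stated rules lead to a cases-only comparison

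*Combined protocol and SAP*

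**What the plan says.** Section 6 lists as a secondary objective "To evaluate time to CDI and/or colonization with" *C. difficile*. Section 7.2.2 turns this into two conditional questions. For infection: "If the patient develops a CDI during the study period, what is the time (in days) from randomization into the study to the CDI". For colonization: "If the patient becomes colonized, what is the time (in days) from randomization into the study to colonization". A patient who never has the event is given no time.

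Section 12.3 is the analysis plan. For quantities such as a number of days it says "Continuous data will be described using means and standard deviations (normally distributed data) or using medians and interquartile range". Comparative tests are to be appropriate ones, selected on "in the variable types (categorical, dichotomous, continuous) and distribution (parametric, non-parametric". The Study Summary (Section 2) adds models for one purpose only: "To assess changes in the gut microbiota, ANCOVA and linear mixed models will be used for longitudinal measurements". Kaplan-Meier, log-rank, Cox regression, cumulative incidence, censoring and competing events are not mentioned anywhere.

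Four other provisions bear on the point:
- Under Section 11.3, CDI ends the patient's participation.
- Under Section 7.2.1, stool sampling stops about one month after the intervention. Section 11.5 puts the last call at 6 months.
- Sections 2 and 7.1 end the intervention 7 days after antibiotics in Groups 1 and 3, and 48-72 hours after antibiotics in Group 2.
- Section 12.2 expects 8 of 10 patients per group to complete treatment and be analyzed.

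**The concern.** Randomization makes the arms comparable as whole groups. It does not make the patients who recur on FMT comparable with those who recur on placebo, because recurrence happens after randomization and may itself be changed by treatment. A mean or median time among cases therefore compares two selected subsets.

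The selection can act against the better arm. If FMT prevents mainly later recurrences, the few that remain on FMT are the early ones, and their average time is short. A reader of that summary alone would see faster recurrence on the arm with fewer recurrences. Late protection is plausible for Group 2, whose only dose comes after antibiotics end although time is counted from randomization. It is less obvious for Group 1, which can be dosed from Day 0 (Section 11.1).

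There is also a plain feasibility problem. With 10 patients per arm, one arm may have no case at all, and then there is nothing to compare.

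**Working it through.** **Stated figures.** The plan gives no power, event count or effect size for this outcome, so there is none to reproduce. The enrollment target is consistent with its own completion goal: 8 / (1 − 0.20) = 10 per group, and 3 × 10 = 30.

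**Inputs from the protocol.** 10 per arm (Section 2); recurrence of 24% to 65% (Section 5.1), used here as a range for placebo risk; follow-up of 6 months (Section 7.1).

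**Assumptions not in the protocol.** Windows of T = 60 or 180 days; a constant placebo hazard; either proportional hazards with HR 0.5 or 0.25, or delayed protection with HR 1 until day 14 or 21 and HR 0.25 afterwards.

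**Formulas.** With placebo risk p, the daily hazard is λ = −ln(1 − p)/T. With S(t) the event-free probability:
- mean event-free time over the window, all patients: RMST = area under S(t) from 0 to T
- mean time among cases only: (RMST − T·S(T)) / (1 − S(T))

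**One case by hand: T = 180, p = 0.24, protection from day 21.**
- λ = 0.2744/180 = 0.001525.
- Placebo: RMST = 0.24/0.001525 = 157.4. Cases-only mean = (157.41 − 180 × 0.76)/0.24 = 85.9 days.
- FMT: cumulative hazard = 21λ + 0.25 × 159λ = 0.0320 + 0.0606 = 0.0926, so risk = 8.8%. RMST = 170.1. Cases-only mean = (170.08 − 164.08)/0.0885 = 67.9 days.

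Simulation at 10 per arm gave 86.0 and 67.7, which agrees within simulation error.

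**Simulated results** (placebo / FMT). Wrong sign means that the cases-only mean is shorter on FMT, among trials where both arms have a case.

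| Setting | Risk | Cases-only mean, days | RMST, days | Wrong sign | An arm has no case |
|---|---|---|---|---|---|
| Delayed, T 60, day 14 | 24% / 11% | 28.6 / 20.0 | 52.5 / 55.6 | 69% | 35% |
| Delayed, T 60, day 21 | 65% / 42% | 24.9 / 17.7 | 37.2 / 42.4 | 76% | 0% |
| Delayed, T 180, day 21 | 24% / 9% | 86.0 / 67.7 | 157.4 / 170.1 | 63% | 44% |
| Delayed, T 180, day 21 | 65% / 30% | 74.5 / 63.9 | 111.4 / 145.3 | 62% | 3% |
| Proportional, T 60, HR 0.5 | 24% / 13% | 28.6 / 29.3 | not needed | 49% | 30% |
| Proportional, T 180, HR 0.25 | 65% / 23% | 74.5 / 86.1 | not needed | 40% | 7% |

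Over all eight delayed settings the sign was wrong in 56% to 76% of computable trials, and 0% to 47% of trials were not computable. Over all eight proportional-hazards settings the figures were 40% to 49% and 1% to 53%.

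**A small data example.** Ten per arm, 180 days. Placebo cases fall on days 10, 25, 45, 60 and 90; FMT cases on days 10 and 20.
- Cases only: 230/5 = 46 days against 30/2 = 15 days, which favors placebo.
- All patients: (230 + 5 × 180)/10 = 113 days against (30 + 8 × 180)/10 = 147 days, which favors FMT.

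**What a censored analysis can deliver.** Approximate log-rank power is Φ(|ln HR|·√(d/4) − 1.96) for d events in one pairwise comparison.
- HR 0.5: 3.7 to 10.6 expected events, power about 10% to 20%; 66 events would be needed for 80%.
- HR 0.25: 3.1 to 8.8 expected events, power about 23% to 54%; 17 events would be needed for 80%.

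**The case against.** A reader might infer that the plan prescribes a cases-only analysis. It does not. Section 7.2.2 is a list of outcomes phrased as questions, and in any survival dataset only patients with an event have an event date. Section 12.3 leaves room for suitable tests, and Section 9.8 commits to intention-to-treat. This much stands: a survival method is not ruled out. But time-to-event is not among the data types listed, and no rule gives patients without the event a time. A statistician who applied the text literally would compare cases.

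A reader might also infer that patients without CDI drop out of the CDI assessment. That is not supported either. Whether CDI occurs is the first half of the same item in Section 7.2.2, and the CDI and colonization rates are separate objectives in Section 6. A report of 24% against 9% would sit beside the times and limit the risk of a reversed conclusion.

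Finally, a reader might infer that the cases-only mean will point the wrong way. Under proportional hazards its expected direction is right, only nearly flat, and wrong signs there are chance. Systematic reversal needs protection that starts late, which the protocol makes plausible for Group 2 but does not establish.

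It is also fair that this is a secondary objective in a pilot not sized for testing (Section 12.1), so a valid method will not produce a decisive test.

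**Conclusion.** The concern holds in this form: the outcome definitions and the only stated analysis rules, taken together, lead to a comparison conditioned on a post-randomization event, and nothing in the plan says how patients without the event enter the time-to-event objective.

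The size depends on assumptions. With delayed protection, all eight settings examined had a shorter expected cases-only time on FMT although FMT lowered risk. With proportional hazards the comparison is close to uninformative. With low risk, an arm often has no case. The hazard ratios, onset days, windows and constant placebo hazard are all assumed; only the 24% to 65% range, the 10 per arm and the 6-month follow-up come from the protocol.

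This should be changed, but it does not threaten the primary microbiota outcome or the CDI occurrence comparison.

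**What to change.** Add to Section 12.3:

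1. **Time to CDI.** Count from randomization in all randomized patients. Use Kaplan-Meier, or cumulative incidence with death as a competing event. Censor patients without CDI at their last CDI assessment.
2. **One assessment window for all arms.** Choose either the end of weekly stool sampling or the 6-month call with symptom- and record-based ascertainment. The two differ by months. For the same antibiotic course, sampling also ends 4 to 5 days earlier in Group 2 (7 days minus 2 or 3). The horizon should therefore be one number of days from randomization that every arm can reach.
3. **Time to incident colonization.** Restrict to patients who are PCR-negative at baseline. Either use an interval-censored estimator or date the event at the first positive sample, and fix that choice now. Censor at the last PCR sample. Treat CDI, which ends participation, and death as competing events.
4. **Reporting.** Show curves by arm and the difference in restricted mean event-free time for each FMT arm against placebo, with 95% confidence intervals. Where competing events are used, the matching quantity is the area under the cumulative incidence curve. Label the results descriptive, given 10 per arm.

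The cost is a few sentences of plan text, a decision on the window and competing events, and a little more analysis work. No new data are needed. The intervals will be wide.

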### **8.2. Inclusion Criteria**

1. Cognitively intact and willing to provide informed consent.
2. Willing and able to comply with all study procedures for the duration of the study.
3. Able to take oral medications.
4. Age 18 or over.
5. Recent CDI episode occurring in the last 90 days with completion of therapy as confirmed by the electronic medical record (EMR)
6. Receiving antibiotics at enrollment for reasons other than CDI and having taken the antibiotics for no longer than 72 hours.
7. Women of childbearing potential in a sexual relationship with men must use an acceptable method of contraception (including, but not limited to, barriers with additional spermicidal foam or jelly, intrauterine devices, hormonal contraception started at least 30 days before enrollment into the study, or intercourse with men who underwent a vasectomy) for 4 weeks following completion of the study treatment.
8. Males must agree to avoid impregnation of women during and for 4 weeks following completion of the study treatment.
9. Able to take the test capsule successfully with no signs or symptoms of dysphagia.\*

\*For patients not receiving treatment during the enrollment visit, the ability to successfully swallow the test capsule can be confirmed the day the intervention is administered.

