## 10. LABS

Tests will not be done in a CLIA-certified lab. Samples will be collected from the patient and brought to the lab while the subject is admitted. After discharge, the subject will mail the samples to the laboratory for processing. Samples will be labeled with only an ID number. We will not disclose any results to the patients. Data generated by the laboratory procedures will be used to determine the patient's colonization status with MDROs and *C. difficile* at baseline and to determine if colonization status changes during the course of the trial.

Laboratory procedures include:

- Bacterial DNA isolation from stool
- 16s rRNA sequencing of the v4 region
- Culture to identify MDROs, including but not limited to: MRSA, Vancomycin-resistant enterococcus (VRE), and *C. difficile*
- Polymerase Chain Reaction (PCR)

Data from laboratory procedures will also be used to determine if the FMT treatment has an impact on the patients gut microbiome. All stool remaining following the completion of laboratory procedures will be stored at -80°C and labeled with the sample ID and held for future analysis.

Up to one gram of stool will be sent to Finch therapeutics for additional 16s rRNA sequencing.

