After the baseline clinical assessment and stool sample have been collected, subjects in groups 1 and 3 (daily FMT and daily placebo) are eligible to undergo administration of the intervention (DE or placebo) in

accordance with the randomization schedule. The intervention will be administered by the blinded treatment staff and the participant observed for 30 minutes following administration. Post-ingestion observation of inpatients will only occur after the first dosing; subsequent inpatient dosing will be administered by a study physician/nurse but do not require 30 minutes of observation. Pre-intervention vital signs (as previously described) will be collected or abstracted from the medical record prior to first dose. Participants will be provided with information regarding monitoring for minor and severe adverse event related to the intervention administration. Participants will be encouraged to report any concerning symptoms to staff. Oral nutrition may commence 1 hour post-capsules administration. Study staff do not need to collect a blood sample to check for neutropenia prior to dosing.

For all patients, a baseline stool sample will be collected and all patients should begin to fill out their patient diary starting on Day 0. If a patient is unable to provide a stool sample, peri-rectal swabs may be collected.

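### The yes/no *C. difficile* colonization outcome can be met by carriage already present at the pre-treatment baseline sample, which dilutes any effect on new colonization

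*Combined protocol and SAP*

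**What the plan says.** Section 7.2.2, item 3, sets the outcome as a single question: "Is the patient colonized or do they become colonized with" *C. difficile* at any time in the study. Detection is by PCR. A second question follows: "If the patient becomes colonized, what is the time (in days) from randomization into the study to colonization".

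Section 6 has two matching objectives. One is the rate of "colonization during oral FMT compared to placebo". The other begins "To evaluate time to CDI and/or colonization with" *C. difficile*. Neither is limited to new colonization.

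Section 8.2, item 5, requires a CDI episode in the last 90 days with therapy completed. Section 8.3 excludes diarrhea (item 14) and current oral vancomycin or metronidazole (item 15), but not symptom-free PCR positivity.

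Section 11.1 provides that "For all patients, a baseline stool sample will be collected", and dosing in groups 1 and 3 comes after it. Group 2 is dosed only after antibiotics end. Section 10 says the laboratory data will give colonization status "at baseline and to determine if colonization status changes during the course of the trial".

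Section 12.3 contains no colonization analysis. It names no at-risk set and no exclusion, stratification or adjustment by baseline status; it says only that appropriate comparative tests will be chosen by variable type and distribution.

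**The concern.** The two halves of the question are joined by *or*. A patient positive at baseline therefore satisfies it before any capsule is taken and cannot later fail to satisfy it. Three things follow.

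- **Dilution.** Patients who can only be counted as colonized carry no information on whether FMT prevents new colonization, yet they sit in both numerator and denominator.
- **Noise.** With 10 patients per arm, a chance difference in carriers moves the observed rates.
- **Lost information.** A carrier who clears *C. difficile* is counted the same as one who stays positive. Section 5.4 gives competitive exclusion of *C. difficile* as the hypothesized mechanism, so clearance is an effect one would want to see.

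The protocol draws this distinction elsewhere: the safety outcomes in section 7.2.3 are limited to events after randomization and to newly acquired infections. Item 3 has no such limit.

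**Working it through.** **Inputs from the documents.** 10 patients per arm (12.1), 8 per arm hoped for in the analysis (12.2), two-sided 0.05 (12.3). The documents give no carriage rate, colonization rate or power for this outcome, so there is no figure of the plan's own to reproduce.

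**Assumptions, for illustration only.** New colonization among baseline-negatives: p = 0.40 on placebo, 0.10 on FMT. Baseline carriage: c = 0.10, 0.30 or 0.50.

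**Step 1: dilution.** Ever-colonized rate = c + (1 − c)p, so the between-arm difference is (1 − c) × 0.30.

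| c | Placebo | FMT | Difference |
|---|---|---|---|
| 0 | 40% | 10% | 30 points |
| 0.10 | 46% | 19% | 27 points |
| 0.30 | 58% | 37% | 21 points |
| 0.50 | 70% | 55% | 15 points |

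At c = 0.30, carriers make up 0.30/0.58 = 52% of placebo events and 0.30/0.37 = 81% of FMT events.

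Assumed rates of 50% and 20% give the same pattern: the difference is 24, 18 or 12 points at carriage of 20%, 40% or 60%.

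**Step 2: chance imbalance.** The SD of the between-arm difference in carriage is √(2c(1 − c)/10) = 13, 20 and 22 points at c = 0.10, 0.30 and 0.50. That is not all added error, because carriage reaches the outcome multiplied by (1 − p), here 0.6 to 0.9. The SD of the outcome difference itself is √([P₁(1 − P₁) + P₂(1 − P₂)]/10), with P₁ and P₂ the ever-colonized rates:

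- c = 0: √(0.33/10) = 18 points
- c = 0.10: √(0.4023/10) = 20 points
- c = 0.30: √(0.4767/10) = 22 points
- c = 0.50: √(0.4575/10) = 21 points

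Noise therefore rises by 2 to 4 points; the loss of difference is the larger effect.

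**Step 3: does restricting to baseline-negatives help, given fewer patients?** The difference is 30 points again, with an expected 9, 7 or 5 patients at risk per arm of 10. Taking those numbers as fixed, the SD is √(0.33/n) = 19, 22 or 26 points. Ratios of difference to SD:

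| c | As worded | Baseline-negatives only |
|---|---|---|
| 0.10 | 27/20.1 = 1.35 | 30/19.1 = 1.57 |
| 0.30 | 21/21.8 = 0.96 | 30/21.7 = 1.38 |
| 0.50 | 15/21.4 = 0.70 | 30/25.7 = 1.17 |

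The restricted outcome is the more informative one throughout this range, though imprecise either way.

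**Step 4: the time question.** It is asked only of a patient who *becomes* colonized, so its wording leaves baseline carriers out. What is missing is a statement of who is at risk: neither 7.2.2 nor 12.3 says whether carriers are removed from the analysis or kept in it without an event.

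**The case against.** The best case for the plan is that item 3 names prevalent and new colonization separately, follows up only the new kind with a time question, and nowhere says the two will be pooled into one comparison. Section 10 plans to measure baseline status and change, and change includes clearance. The trial is a 30-patient pilot not sized on a hypothesis test; with assumed rates of 50% and 20%, Fisher power at 10 per arm is only 13% even with no carriers.

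Much of this stands. It limits the practical effect to interpretation of a secondary outcome, and it shows that the data for a better definition will exist. It does not remove the problem. Item 3 gives one question and one detection rule, and no outcome or analysis takes up the purpose stated in section 10 ("to determine if colonization status changes during the course of the trial"). A pilot's descriptive rates are its product, and section 12.3 also plans testing at 0.05.

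Stronger readings that a reader might infer, but that the documents do not support:

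- *Carriers enter the time analysis at day zero.* The time question is conditional on becoming colonized.
- *Baseline status is fixed before randomization.* The section 3 schematic puts baseline on Day 0 and randomization on Day 1, but section 11.1 allows randomized dosing at the Day 0 visit. Only *before treatment* is secure.
- *The comparison is systematically biased between arms.* Randomization balances carriage in expectation. The effects are dilution and chance imbalance.
- *The plan scores clearance as failure.* No success or failure scoring exists for this outcome; the wording simply does not separate clearance from persistence.

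**Conclusion.** The point holds for the yes/no outcome. As worded, pre-treatment carriage meets it, and nothing in section 12.3 removes or adjusts for that. The true difference in new colonization is multiplied by (1 − baseline carriage): on the assumed 30 points, 27, 21 or 15 at 10%, 30% or 50% carriage, with a modest rise in noise. Actual carriage is unknown. Recent CDI in every participant makes it plausible, while completed therapy and the exclusion of diarrhea leave its frequency open. For time to colonization, the only defect is the unstated at-risk set. This should be corrected, but it concerns a secondary outcome in an unpowered pilot.

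**What to change.** Amend sections 7.2.2 and 12.3, before unblinding, to define:

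1. **Incident colonization**, and time to it from randomization, among patients PCR-negative at baseline. State this as the at-risk set.
2. **Clearance or persistence** among patients PCR-positive at baseline. This carries out the change-in-status purpose already in section 10.
3. For **any comparison of all randomized patients**, post-baseline status adjusted for baseline PCR status, with a stated rule for patients whose follow-up ends early because of CDI. Sections 11.3 and 11.4 end participation and stop study procedures on CDI, apart from an attempted final stool sample, so later samples may be missing for exactly these patients.

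The change uses the baseline stool already planned, so it needs no new visit or sample. It is a change to protocol text as well as to the analysis plan, because 7.2.2 is the outcome definition. The price is small denominators. At 10%, 30% or 50% carriage, about 9, 7 or 5 baseline-negatives are expected per arm of 10 (7.2, 5.6 or 4.0 per arm of 8), with the remainder in the clearance subset. Both subset results should be reported as descriptive, with counts and confidence intervals.
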